Lipodystrophies, in which there is partial or complete absence of adipose tissue (and hence, adipokines such as leptin), represent another model for understanding the actions of leptin in a state of deficiency and replacement. Unlike patients with congenital leptin deficiency, patients with lipodystrophy are non-obese, but have more extreme manifestations of the metabolic syndrome due to factors such as ectopic lipid storage^{22,23}. Leptin replacement in lipodystrophy reduces food intake^{24,25} and ameliorates most metabolic abnormalities, including insulin resistance^{25,27} and diabetes^{26,28,29}, hypertriglyceridemia^{27,29}, and hepatic steatosis^{25,30}. Based on data derived largely from studies conducted in the intramural research program of the NIDDK, the FDA approved metreleptin (recombinant methionyl leptin) for the treatment of generalized lipodystrophy in February, 2014; however, leptin remains an experimental therapy in other forms of lipodystrophy, including partial lipodystrophy.

Limited information is available about the time course of leptin's effects in lipodystrophy. In seven patients with generalized lipodystrophy, declines in glucose and triglyceride levels reached statistical significance by 7 days after leptin initiation³¹. In these subjects, non-significant increases in insulin sensitivity (measured using the hyperinsulinemic, euglycemic clamp) were seen one month after starting leptin, and significant increases after 2 months.

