More detailed mechanistic studies of leptin's effects on glucose and lipid metabolism after 3-8 months have been performed on three patients with lipodystrophy (one acquired generalized and two congenital generalized)²⁵. Using stable isotope infusions in combination with the hyperinsulinemic, euglycemic clamp, these subjects in the leptin deficient state were shown to have elevated hepatic glucose production and severe hepatic insulin resistance compared to healthy controls. After leptin replacement for 3-8 months, hepatic insulin resistance decreased to nearly that of controls, and insulin-stimulated glucose disposal doubled. These changes were associated with an 86% reduction in hepatic triglyceride content and a 33% reduction in muscle triglyceride, suggesting that reduction in ectopic lipid may have contributed to the improvements in insulin sensitivity. Non-significant decreases in glycerol turnover were also observed following leptin treatment, suggesting that leptin increased lipolysis in any existing adipose tissue or within ectopic lipid stores. In a single subject, a 30% reduction in muscle fatty acyl CoA levels was observed after leptin replacement, offering support for the hypothesis that these compounds contribute to insulin resistance by interfering with insulin receptor substrate-1 (IRS-1) tyrosine phosphorylation, a key step in the insulin signaling cascade. In summary, leptin appears to improve plasma glucose and triglycerides within 1 week, while improvements in insulin sensitivity may be detectable by one month, with continued improvement thereafter, and changes in ectopic lipid storage may not be detectable for several months after leptin initiation.

The effect of leptin on lipid metabolism has also been examined in a randomized, controlled trial of leptin for 4 months in 17 men with HIV associated lipodystrophy³². In this trial, the authors did not find any effects of leptin treatment on lipid metabolism, including fasting triglycerides, rates of lipolysis, and fatty acid oxidation. This suggests that there may be differences in the effect of leptin on lipid metabolism in HIV patients versus the non-HIV infected population studied at NIH. These differences may be related to the severity of the phenotype (typically milder in HIV) or to the doses of leptin used in the HIV study (0.02-0.04 mg/kg/day, which is 25-50% of the lowest doses used in NIH studies).

Energy intake independent effects of leptin

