Sympathetic nervous system tone ¹¹ (% Δ in mean ECG R-R interval after atropine + esmolol vs. atropine alone)	10% wt loss	5 wk	-25% (22.1)	1% (1.6)	0.98	0.97
Liver volume ²⁴ (cm ³)	lipodystrophy	4 mo	3055 (1051)	2433 (763)	0.45	0.29
Total body insulin sensitivity ³¹ (glucose infusion rate during clamp, mg*kg ⁻¹ *min ⁻¹)	lipodystrophy	1 mo	2.5 (0.79)	3.7 (1.1)	0.87	0.63
Total body insulin sensitivity ²⁵ (glucose infusion rate during clamp, mg*kg ⁻¹ *min ⁻¹)	lipodystrophy	4 mo	1.2 (0.35)	5.4 (1.6)	1	1
Hepatic insulin sensitivity ²⁵ (% suppression of endogenous glucose production during clamp)	lipodystrophy	4 mo	40 (10.4)	82 (8.7)	1	1
Fasting glucose ³¹ (mg/dL)	lipodystrophy	7 d	172 (20)	120 (12)	1	0.99
Fasting triglycerides ³¹ (mg/dL)	lipodystrophy	7 d	700 (272)	260 (98)	0.99	0.98
Fasting triglycerides ³¹ (mg/dL)	lipodystrophy	14 d	700 (272)	110 (38)	1	0.99
Rate of lipolysis ²⁵ (glycerol turnover, μmol*kg fat mass ⁻¹ *min ⁻¹)	lipodystrophy	4 mo	78 (36)	25 (7)	0.99	0.99

Based on these calculations, a sample size of 10 subjects in each group (leptin-naïve and leptin-treated) will provide greater than 80% power (in most cases greater than 95%) for the following primary and secondary outcomes:

Glucose Metabolism

1. Total body insulin sensitivity
2. Hepatic insulin sensitivity
3. Fasting plasma glucose

Lipid Metabolism

1. Rate of lipolysis
2. Fasting triglycerides

Energy Expenditure

1. Total energy expenditure
2. Skeletal muscle work efficiency

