Exploratory outcomes for which we anticipate greater than 80% power include epinephrine and sympathetic nervous system tone. Discrepant data exist for the effects of leptin on thyroid function (specifically, T3) based on the model used (lipodystrophy versus 10% weight loss), and this study should help to clarify whether this effect does or does not exist in lipodystrophy. We do not anticipate observing significant changes in resting energy expenditure; however, because this procedure is minimal risk, we feel that it will be important to document negative results for this outcome. Certain outcome measures, such as liver triglyceride (for which liver size was a proxy in the table, above), and insulin sensitivity, appear to progressively change over time with leptin replacement. For these outcomes, a 2 week intervention may be insufficient to observe statistically significant results. For other outcome measures, such as intramyocellular triglyceride, preliminary data on the short-term effects of leptin are not available, but effects, if present, are unlikely to be detectable by two weeks.

Therefore, in addition to obtaining data after 2 weeks of leptin withdrawal or initiation, we will restudy subjects in the leptin-naïve group 6 months (range is 5-9 months) after leptin initiation to look for changes that may not be detectable by 2 weeks.

Because some subjects may not complete the study, or may not have interpretable data for each outcome, we plan to enroll up to 20 subjects in each group in order to have 10 completers per group.

Statistical Methods for Data Analysis

Data will be analyzed separately for the leptin naïve and leptin treated subjects. This is done because the effects of leptin withdrawal after long-term treatment are likely to be different from the effects of leptin initiation after long-term deficiency.

Analysis of Primary Outcomes

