Measurements in each of the primary outcomes will be analyzed using the paired t-test (for normally distributed variables) or Wilcoxon paired test (for skewed variables) to test if there is any significant difference between the two study periods (on and off leptin) for each group (leptin naïve and leptin treated), respectively. In addition, mixed models incorporating baseline (pre-diet) parameters as covariates will be used to adjust for any effects of the inpatient, metabolic diet, independent of leptin's effects. For variables with more than 2 measurements during Period 2, repeated measure linear models (Mixed model or GLM) will be used to study the time effect, using pooled data from the 2 periods. Potential covariates to be explored in the model include: Age, sex, race, percent body fat, lean mass, body weight, type of lipodystrophy, and endogenous leptin level. To account for any deviation from the isocaloric protocol diet, actual caloric intake will be included as a covariate in mixed model analyses.

Additional correlations between variables within and between each of the major outcome categories (glucose metabolism, lipid metabolism, and energy expenditure) will be analyzed using either Pearson's correlation or simple linear regressions. These include the following:

1. Association between change in total body insulin sensitivity and changes in hepatic insulin sensitivity, fasting plasma glucose, and C-peptide
2. Association between change in rate of lipolysis, and changes in fasting triglycerides and fatty acid turnover
3. Association between insulin sensitivity and ectopic lipid stores, and rates of lipolysis and fatty acid turnover
4. Association between change in total energy expenditure and changes in resting energy expenditure, skeletal muscle work efficiency, spontaneous physical activity, thyroid function, catecholamines, and cardiac autonomic nervous system tone.

Analysis of Secondary and Exploratory Outcomes

Methods for analysis of secondary outcomes will be similar to those for primary outcomes. In addition, we will perform analysis to study the following associations between categories of outcome measures:

1. Association between the Ectopic Lipid measurements with Glucose and Lipid measurements
2. Association between the Endocrine measurements with Energy Expenditure measurements

Analysis of long-term data

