Subjects will undergo metabolic and endocrine testing at the end of Period 1 and at the end of Period 2. Certain tests will also be performed at earlier time points during Period 2, in order to clarify the time course of leptin initiation and withdrawal on these outcomes. Explanations for the timing of these tests are provided in the detailed test descriptions. A summary of the test schedule is in the table, below. Tests associated with Period 1 and the follow-up are highlighted in gray. The exact timing of each test may vary slightly due to practical scheduling issues. A sample patient calendar is given in Appendix A.

Study Day	Period 1					Period 2														
	-5	-4	-3	-2	-1	0	1	2	3	4	5	6	7	8	9	10	11	12	13	14
Metabolic Chamber					x							x						x		
24 hr urine					x							x						x		
DEXA						x													x	
Skin temperature			x		x						x					x		x		
Exercise test			x								x					x				
Resting Energy Expenditure	x			x			x				x				x		x			
Blood pressure monitoring				x	x	x	x										x	x		
Heart rate monitoring				x	x	x	x										x	x		
Euglycemic Clamp				x													x			
Glucose & lipid turnover				x								x					x			
LH pulsatility			x														x			
MRI/MRS				x													x			
Fasting research blood tests	x				x	x		x		x		x		x		x		x	x	
Safety labs	x				x	x		x		x		x		x		x		x	x	
Actigraphy			x	x	x	x	x	x	x	x	x	x	x	x	x	x	x	x	x	
Vital signs	x	x	x	x	x	x	x	x	x	x	x	x	x	x	x	x	x	x	x	x
Anthropometrics	x					x													x	
Bedside glucose monitoring	x	x	x	x	x	x	x	x	x	x	x	x	x	x	x	x	x	x	x	x
Pregnancy test	x																x			
Echocardiogram		x																		
Ultrasounds	x			x																
OGTT	x																			

Long-term follow-up

Certain effects of leptin may not be detectable, or may be submaximal, within the 2-week intervention period in this study. These include changes in liver steatosis and insulin sensitivity. For this reason, we wish to study the longer-term (6 months) effects of leptin in subjects participating in this study. Therefore, we plan to restudy subjects in the leptin naïve group and bring them in for follow-up 6 months (range, 5-9 months) after starting leptin. Given budgetary and logistical issues, foreign patients may be seen for follow-up 12 months after initiating leptin therapy. We will ask them to obtain lab work locally and send us the results. It will not be possible to maintain an isocaloric diet for 6 months after leptin initiation in the free-living environment.

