Therefore, long-term follow-up data on leptin's effects will not help to answer questions about the energy intake independent effects of leptin. Nonetheless, these data will provide valuable additional information about the time course of leptin's actions in lipodystrophy. Testing during the follow-up visits will mimic that performed during Period 1.

Metabolic Testing

1. Exercise testing: Testing will be performed at the end of Period 1, in the middle and end of Period 2, and during the long-term follow-up visit for subjects in the leptin-naïve group. Skeletal muscle work efficiency will be measured as the increment in energy expenditure above resting energy expenditure during exercise, with lower incremental increase in energy expenditure corresponding to greater muscle work efficiency. This test will be conducted on a cycle ergometer. Following a 10 minute warm-up period, subjects will pedal at 60 rpm with the resistance adjusted to generate 10W of power for 4 minutes. The resistance will then be increased such that the power generated is 25W for 4 minutes, then 50W for 4 minutes. Breath-by-breath oxygen consumption and carbon dioxide production will be collected and averaged every 30 seconds using a metabolic cart (ParvoMedics TrueOne2400, Sandy UT). Heart rate will be monitored by electrocardiograph.
2. Free-living physical activity (actigraphy) will be quantified minute-by-minute using small, portable pager-type and watch accelerometers at the subjects' hip and wrist. Overall physical activity levels, daily changes, amount of time spent in sedentary, moderate, vigorous intensity categories and activity-associated energy expenditures will be extracted [35]. Actigraphy will be conducted continuously throughout the study, beginning on Day -5, and ending on Day 14, and during the long-term follow-up visit for subjects in the leptin-naïve group

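### The over-80% power stated for clamp insulin sensitivity, a primary outcome, rests on 1-month and 3-8-month effects, while the plan itself doubts that two weeks is long enough to detect a change

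*Combined protocol and SAP*

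**What the plan says.** Outcome Measures (combined protocol and SAP) makes the clamp glucose disposal rate the primary outcome for glucose metabolism. Sample Size Justification sets the primary comparison as end of Period 1 against end of Period 2, separately in each group. From the Methods and Design text, that is 14 days of leptin initiation or withdrawal on an isocaloric diet.

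The power table has two rows for this outcome, at 1 month and at 4 months. The text below it concludes that "a sample size of 10 subjects in each group (leptin-naïve and leptin-treated) will provide greater than 80% power" for a list headed by total body insulin sensitivity.

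Other parts of the document point the other way:

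- Sample Size Justification, after the list, on outcomes that change progressively, insulin sensitivity among them: "For these outcomes, a 2 week intervention may be insufficient to observe statistically significant results".
- Long-term follow-up: certain effects may not be "detectable, or may be submaximal, within the 2-week intervention period in this study. These include changes in liver steatosis and insulin sensitivity".
- Leptin in lipodystrophy, on the source of the 1-month row: "non-significant increases in insulin sensitivity (measured using the hyperinsulinemic, euglycemic clamp) were seen one month after starting leptin, and significant increases after 2 months". The same section sums up: "while improvements in insulin sensitivity may be detectable by one month, with continued improvement thereafter".
- The same section, on the source of the 4-month row: mechanistic studies "after 3-8 months have been performed on three patients with lipodystrophy".
- Long-term follow-up, on the 6-month restudy of the leptin-naïve group: such data "will not help to answer questions about the energy intake independent effects of leptin".

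**The concern.** The power statement and the caveat concern the same outcome at the same time point, and they do not agree. The statement applies to day 14 an effect measured at one month or later. It also makes no allowance for fixed intake, although the section on energy-intake-independent effects considers lower intake a likely contributor to the published glucose changes. That section counts only two human studies of intake-independent effects, and the two clamp sources are not among them. So they appear not to have controlled intake, though this is an inference.

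What is at stake is how a null result is read. The null hypothesis is that leptin has no effect at fixed intake, and day 14 is the only clamp comparison made after a change in leptin at fixed intake. A reader who trusts the stated power could take a non-significant day-14 clamp as support for that null when the study may not have been able to detect the effect.

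**Working it through.** **Inputs** (power table): 1-month row, off leptin 2.5 (SD 0.79), on leptin 3.7 (SD 1.1) mg/kg/min; 4-month row, 1.2 (0.35) and 5.4 (1.6). n = 10 pairs, alpha 0.05, sidedness not stated.

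**Reproducing the printed figures, 1-month row**

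- Effect: 3.7 − 2.5 = 1.2.
- First power column (independent SDs): SD of the difference = √(0.79² + 1.1²) = 1.354; standardised effect 1.2/1.354 = 0.886.
- One-sided normal approximation: Φ(0.886 × √10 − 1.645) = 0.876, against 0.87 printed.
- Second power column: the printed 0.63 is approached by taking the SD of the difference as the sum, 0.79 + 1.1 = 1.89, which gives 0.642. The text describes perfect positive correlation, but a sum of SDs corresponds to perfect negative correlation.
- A two-sided paired t-test (noncentral t, 9 df) gives 0.704 on the first SD and 0.434 on the second.

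The printed values therefore match a one-sided normal calculation for the full 1-month effect. Analysis of Primary Outcomes plans a paired t-test (Wilcoxon if skewed) "to test if there is any significant difference between the two study periods (on and off leptin"), which reads as two-sided. The two-sided paired t is used from here on.

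**Power at day 14.** The documents give no day-14, fixed-intake clamp effect. The shares and correlations below are assumptions that show the range. SD of the difference = √(0.79² + 1.1² − 2ρ × 0.79 × 1.1); the last column is the difference needed for 80% power.

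| Within-person correlation ρ (1-month row) | SD of difference | Power at 100% / 75% / 50% of 1.2 | Difference for 80% power |
|---|---|---|---|
| 0 (first power column) | 1.354 | 0.70 / 0.47 / 0.24 | 1.35 |
| 0.3 | 1.146 | 0.84 / 0.60 / 0.32 | 1.14 |
| 0.5 | 0.982 | 0.93 / 0.73 / 0.41 | 0.98 |
| 0.7 | 0.786 | 0.99 / 0.90 / 0.58 | 0.78 |

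At zero correlation the required difference is 1.349/1.2 = 112% of the 1-month effect.

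**4-month row.** Effect 5.4 − 1.2 = 4.2; SD of the difference √(0.35² + 1.6²) = 1.638. Half the effect (2.1) gives power 0.95, 40% (1.68) gives 0.82, and 25% (1.05) gives 0.44.

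**Precision.** Expected 95% CI half-width at SD 1.354: 2.262 × 1.354/√10 = 0.97 mg/kg/min.

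**The case against.** The strongest reply is that the plan discloses this. The study is called exploratory, the list is tied to the calculations above it, the table prints model and duration, and the caveat follows in the same section. All of that stands, so it would be wrong to infer that the limitation is concealed. What remains is that the caveat does not change the listed claim, which still says over 80% for this outcome.

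A reader might also infer that the trial is underpowered for insulin sensitivity. The documents do not show that. Power depends on an unknown day-14 effect and an unknown within-person correlation, and both could be favourable, as the table and the 4-month row show. The starting dose in the naïve group was chosen to raise the chance of a two-week effect, and one patient's serum insulin rose after four days of withdrawal at constant intake. Neither supplies a day-14 clamp effect size.

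Nor does the non-significant 1-month result in the source study refute the printed 0.87. It came from seven patients, and the same inputs at n = 7 give power of only 0.50 (two-sided t) or 0.76 (one-sided normal).

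Finally, it is tempting to apply the contradiction equally to both groups. The caveat is written about leptin replacement, and the plan expects withdrawal to behave differently. For the leptin-treated group the fair statement is narrower: its power rests on initiation data.

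**Conclusion.** The concern holds as an inconsistency in the stated power. The over-80% claim for this primary outcome depends on effects from 1 month and from 3-8 months (three patients), whereas the comparison is at 14 days and fixed intake, and the plan itself says two weeks may be too short. The table's second power column, 0.63 on the 1-month row, falls below 80% without any assumed share. It corresponds to an extreme correlation, so it is not a likely value, but it is the plan's own conservative figure.

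Day-14 power is unknown. On the 1-month row with independent SDs it is 0.70 even for the full effect, and 0.24 for half of it. Within-person correlation or a larger effect would raise these values. The 6-month restudy does not settle the matter, because intake is not controlled by then and only the naïve group is restudied. The conflict is clearest for the leptin-naïve group.

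**What to change.** In Sample Size Justification, either remove total body insulin sensitivity from the over-80% list for the two-week comparison, or keep it with an explicit condition and a cross-reference to the caveat that follows. Use one method throughout. Suggested content: with 10 completers, a two-sided paired t-test and the independence-based SD of 1.354, 80% power needs a day-14 difference of about 1.35 mg/kg/min, or 112% of the 1-month effect. Label this as the zero-correlation case and give the range (about 1.14, 0.98 and 0.78 at assumed correlations of 0.3, 0.5 and 0.7). Note that the leptin-treated group's figure is borrowed from initiation data.

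In Analysis of Primary Outcomes, add that the day-14 clamp change will be reported with a 95% CI, and that a non-significant result is not by itself evidence of no intake-independent effect.

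The cost is wording only: no added patients, no new procedures and no change to the tests. The stated power for one primary outcome becomes conditional.
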